11.2 Adverse Events

The Investigator is responsible for monitoring the safety of patients who have enrolled in the study and for accurately documenting and reporting information as described in this section. Patients will be instructed to report to the Investigator any AE that they experience. Investigators will ask about the occurrence of AEs at each visit. Investigators are required to document all AEs occurring during the clinical study, commencing with the first dose of IMG-7289 through to the End of Study Visit (scheduled at 28 days post last IMG-7289 dose). Adverse event recording will continue for patients

who discontinue study treatment early but remain in follow-up, until their End of Treatment, Pre-End of Study and End of Study Visits have been completed.

Note: Any medical event which occurs from the time of Informed Consent but prior to dosing with IMG-7289 must still be documented in the patient's medical notes and will be recorded on the appropriate medical history CRF pages.

Adverse events will be recorded on designated CRF pages. Each AE is to be characterised (i.e., verbatim term) and information provided regarding its seriousness, start and stop dates, intensity, outcome, and causal relationship with the study drug.

An AE is any undesirable physical, psychological or behavioral effect experienced by a patient during participation in an investigational study, in conjunction with the use of the drug or biologic, whether or not product-related. This includes any untoward signs or symptoms experienced by the patient from the time of first dose with IMG-7289 until completion of the study.

Adverse events may include, but are not limited to:

- Subjective or objective symptoms spontaneously offered by the patient and/or observed by the Investigator or medical staff
- Findings at physical examinations
- Laboratory abnormalities of clinical significance

Progression of underlying malignancy is not reported as an AE if it is consistent with the suspected progression of the underlying cancer. Clinical symptoms of progression may be reported as AEs if the symptom cannot be determined as exclusively due to the progression of the underlying malignancy or does not fit the expected pattern of progression for the disease under study. If there is any uncertainty about an AE being due to only the disease under study, it should be reported as an AE.

It is important that Investigators record accurate AE terms on CRFs. Wherever possible, a specific disease or syndrome rather than individual associated signs, symptoms or laboratory parameter will be identified by the Investigator and recorded on the CRF. However, if an observed or reported sign, symptom or laboratory parameter is not considered a component of a specific disease or syndrome by the Investigator, or is atypical, it should be recorded as a separate AE on the CRF.

Disease signs, symptoms, and/or laboratory abnormalities already existing prior to the use of the investigational product are not considered AEs after treatment unless they reoccur after the patient has recovered from the preexisting condition or in the opinion of the Investigator they represent a clinically significant exacerbation in intensity or frequency.

Clinical significance is defined as any variation in signs, symptoms, or testing that has medical relevance and may result in an alteration in medical care. The Investigator will continue to monitor the patient until the assessment returns to Baseline or until the Investigator determines that follow-up is no longer medically necessary.

11.2.1 Adverse Event Intensity

Adverse event intensity will be evaluated using the National Cancer Institute (NCI) Common Terminology Criteria for Adverse Events (CTCAE) version 4.03, published 14 June 2010. For AEs not included in the NCI CTCAE, the Investigator will be required to assess the intensity of the adverse drug/biologic experience using the following categories and associated guidelines:

- Grade 1: Mild; asymptomatic or mild symptoms; clinical or diagnostic observations only; intervention not indicated
- Grade 2: Moderate; minimal, local or noninvasive intervention indicated; limiting age-appropriate instrumental ADL*
- Grade 3: Severe or medically significant but not immediately life-threatening; hospitalization or prolongation of hospitalization indicated; disabling; limiting self-care ADL**
- Grade 4: Life-threatening consequences; urgent intervention indicated
- Grade 5: Death related to AE.

Note 1: A semi-colon indicates 'or' within the description of the grade.

Note 2: Activities of Daily Living (ADL)

*Instrumental ADL refer to preparing meals, shopping for groceries or clothes, using the telephone, managing money, etc.

**Self-care ADL refer to bathing, dressing and undressing, feeding self, using the toilet, taking medications, and not bedridden.

11.2.2 Adverse Event Relatedness

The Investigator will make a judgment regarding whether or not, in his/her opinion, the AE was related to study drug. The Investigator will also evaluate any changes in laboratory values, make a determination as to whether the change is clinically significant, and whether or not the change(s) were related to study drug. However, even if the Investigator feels there is no relationship to the study drug, the AE or clinically significant laboratory abnormality MUST be recorded on the CRF. Below are guidelines for relationship assessment:

- Unrelated: There was no relationship of the adverse event to the use of the drug or biologic. This may include, but is not limited, to the adverse experience being an expected outcome of a previously existing or concurrent disease, concomitant medication or procedure the subject experienced during their treatment period.
- Remote/Unlikely: Adverse events which are judged probably not related to the drug or biologic.
- Possible: There was no clear relationship of the adverse event to the use of the drug or biologic; however, one cannot definitively conclude that there was no relationship.

- Probable: While a clear relationship to the drug or biologic cannot be established, the event is associated with an expected adverse event (per the current Investigator Brochure or DSMC findings) or there is no other medical condition or intervention which would explain the occurrence of such an experience.
- Definite: The relationship of the use of the drug or biologic to the experience is considered definitively established.

If a causal relationship is considered probable, possible, or definite by the Investigator, the AE is considered to be “related” for purposes of regulatory reporting. If a causal relationship is considered remote/unlikely or unrelated, the AE is considered “unrelated” for purposes of regulatory reporting.

11.2.3 Serious Adverse Events

Serious adverse events will be reportable from the time the time of first dose through the End of Study Visit (scheduled for approximately 28 days post last IMG-7289 dose) **or** until the Investigator and Imago BioSciences determine that follow-up is no longer necessary. Serious adverse events that are suspected to be drug related will be reported even if they occur when the patient is no longer on the study.

An SAE is any AE that results in any of the following outcomes:

- Death[‡]
- Life-threatening experience
- Required or prolonged inpatient hospitalisation[‡]
- Persistent or significant disability/incapacity
- Congenital anomaly
- Important medical events that, based upon appropriate medical judgment, may jeopardise the patient and may require medical or surgical intervention to prevent one of the outcomes listed above.

Life-threatening experience. Any adverse event that places the patient, in the view of the reporter, at immediate risk of death from the adverse event as it occurred, i.e., does not include an adverse event that had it occurred in a more severe form, might have caused death.

Required or prolonged inpatient hospitalisation. The adverse event resulted in an initial inpatient hospitalisation or prolonged an existing hospitalisation of the patient. If a patient is hospitalised as part of the clinical use of the product, a period of normal hospitalisation will be outlined in the protocol or by the judgment of the Investigator. Hospitalisations longer than this period will be prolonged hospitalisations.

Persistent or significant disability/incapacity. An adverse event that resulted in a substantial disruption of a person’s ability to conduct normal life functions.

Congenital Anomaly. The exposure of the patient to the drug or biologic during pregnancy that is

judged to have resulted in the congenital anomaly/birth defect.

Important medical events. Adverse events that may not result in death, be life-threatening, or require hospitalisation may be considered a serious adverse event when, based upon appropriate medical judgment, may jeopardise the patient or subject and may require medical or surgical intervention to prevent one of the outcomes listed above. Important medical events or interventions may be considered an SAE based upon medical judgment of the Investigator.

‡**Note:** Hospitalization consistent with progression of underlying malignancy should NOT be reported as an SAE. An SAE with an outcome of death solely due to progression of the underlying malignancy does not need to be reported as an SAE.

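### The Section 11.2.3 note exempts hospitalisation from SAE reporting on a looser test than death, so a possibly drug-related admission can miss the 24-hour report

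*Protocol*

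**What the plan says.** Protocol Section 11.2.3 defines seriousness by outcome: "An SAE is any AE that results in any of the following outcomes". The list includes death and required or prolonged inpatient hospitalisation, and both carry the marker of a note. The note has two sentences:

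- Hospitalisation: "Hospitalization consistent with progression of underlying malignancy should NOT be reported as an SAE".
- Death: "An SAE with an outcome of death solely due to progression of the underlying malignancy does not need to be reported as an SAE".

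The other criteria (life-threatening, disability, congenital anomaly, important medical event) carry no exemption. The important-medical-event criterion is discretionary: "Important medical events or interventions may be considered an SAE based upon medical judgment of the Investigator".

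Three other sections bear on the point:

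- **Section 11.2** says that progression is not an AE when it is consistent with the suspected course of the cancer. It then adds a tie-break: "If there is any uncertainty about an AE being due to only the disease under study, it should be reported as an AE".
- **Section 11.2.2** rates an event as possible when "one cannot definitively conclude that there was no relationship". The sentence beginning "If a causal relationship is considered probable, possible, or definite by the Investigator" goes on to class such an AE as related for regulatory reporting.
- **Section 11.2.4** requires a report within 24 hours of awareness, whatever the relatedness, once the Investigator decides that the SAE definition is met.

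**The concern.** The two sentences of the note set different tests. Death needs progression to be the sole cause, and the exemption is permissive. Hospitalisation needs only to be consistent with progression, and the instruction not to report is mandatory. The broader and firmer exemption therefore sits on the non-fatal events, and nothing in it asks whether the drug may have contributed.

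SAEs are part of the primary safety endpoint (Protocol Section 12.4.1; SAP Section III.A). An admission dropped by the note would be missing from the SAE tabulation and would not reach the sponsor by the 24-hour route. In this trial the drug's expected effects and the disease's progression can look alike. Patients after the sentinel are enrolled on a rolling basis (Protocol Section 5.1), so prompt notice has practical value.

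**Working it through.** No arithmetic applies. The check sets the clauses side by side and follows one admission through them.

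**The two tests**

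| | Hospitalisation | Death |
|---|---|---|
| Link to progression | consistent with | solely due to |
| Force | should not be reported | need not be reported |
| Relatedness condition | none | none stated, but sole cause leaves no room for the drug |

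**Can an event be exempt and also possibly related?** A possible rating requires only that a drug relationship cannot be ruled out. An event solely due to progression cannot meet that. An event merely consistent with progression can. Only the hospitalisation sentence lets the two classifications coexist.

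**Tracing a non-fatal, non-life-threatening admission rated possibly related**

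1. Section 11.2: there is uncertainty about the cause, so the event is recorded as an AE.
2. Section 11.2.2: the rating makes it a related AE for regulatory purposes.
3. Section 11.2.3, list: inpatient hospitalisation meets a seriousness criterion.
4. Section 11.2.3, note: if the admission is consistent with progression, it is not to be reported as an SAE. The relatedness rating does not change this.
5. Section 11.2.3, remaining criteria: SAE status survives if another criterion applies. For most such admissions the relevant one is the important-medical-event criterion, which depends on the Investigator's judgement.
6. Section 11.2.4: if no other criterion is applied, the 24-hour duty does not start.
7. Section 14.4: the AE is entered on the CRF, on average within 5 business days of the study visit.

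**Where drug effect and progression overlap.** Section 8.2.1 says that loss of LSD1 activity halts formation of red cells, platelets and granulocytes, and expects doses that cause profound thrombocytopenia and neutropenia.

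- *MDS (Table 15).* Besides its blast criteria, disease progression has three items: a fall of at least 50% from maximum response in granulocytes or platelets, an Hgb fall of at least 2 g/dL, and transfusion dependence. The failure category also mentions worsening cytopenias.
- *AML (Table 14).* Progressive disease is defined by marrow or peripheral blasts, with no count or transfusion item.

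The overlap is therefore greater in MDS. It concerns mainly clinical consequences such as bleeding or infection, because Section 8.2.1 treats the expected cytopenias themselves as not adverse and some leave the AE pathway before the note applies.

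**The case against.** The strongest reply is that Section 11.2 uses the same phrase. There, progression consistent with the suspected course of the cancer is the category that is not an AE at all, and next to it stands a test of whether the event is due exclusively, or only, to the disease. The hospitalisation sentence also speaks of hospitalisation rather than of an AE or SAE. On that reading the note covers only admissions for progression that never became AEs, and a possibly related event is uncertain by nature and falls outside it.

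This is a fair, harmonised reading, and many sites may apply it. The text does not compel it. The note is attached by its marker to a criterion for events that are already AEs, it does not repeat the tie-break, and the tie-break promises AE recording, not SAE reporting.

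Other points that stand:

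- Table 15's granulocyte and platelet item is measured from maximum response, not from baseline, and the note does not cite the table. A reader might infer that any drug-induced fall in counts is MDS progression; the table does not say so.
- The sponsor has other routes to the information. The Medical Monitor is consulted on dose changes for AEs and for clinically significant platelet or neutrophil changes (Sections 7.2.2 and 8.2.1). The Medical Monitor and DSMC are consulted on interruption, reduction and re-challenge (Section 8.3). The DSMC reviews AEs (Section 8.1), the sponsor may escalate an AE to a medical event of interest (Section 11.2.5), and the synopsis says febrile neutropenia admissions will be assessed.
- Fatal and life-threatening events go to the sponsor immediately (Section 11.2.4).
- The detailed SAE procedure is in the Study Reference Manual, which is not among the documents and may already settle the point.

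These narrow the problem. None guarantees a prompt report of a possibly related, non-life-threatening admission that the Investigator reads as consistent with progression.

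**Conclusion.** The concern holds in a limited form. Read literally, the note lets an admission lose SAE status on the hospitalisation criterion, and with it the 24-hour report, when the event is non-fatal and non-life-threatening, resembles progression, is rated possibly related or higher, and is not judged an important medical event. This rests on the literal reading and on the Study Reference Manual not saying otherwise.

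Four stronger readings are tempting, and the documents do not support them:

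- *Events vanish from the safety data.* They do not: Section 11.2 keeps uncertain cases as AEs.
- *Dose escalation is compromised.* The DLT definition in Section 8.2.1 does not depend on SAE status, so the Cycle 1 rule is not directly changed.
- *The report arrives a stated number of days late.* The SAE limit is a maximum of 24 hours from awareness; the CRF figure is an average of 5 business days from a visit. Subtracting one from the other gives neither a bound nor a mean delay.
- *Expedited regulatory reports are missed.* That turns on expectedness in the Investigator's Brochure, which is not available here.

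Neither the number of affected admissions nor the length of delay can be quantified from the documents.

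**What to change.** Replace the hospitalisation sentence of the note with:

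> *Hospitalization solely due to progression of the underlying malignancy need not be reported as an SAE; if there is any uncertainty, or the AE leading to admission is rated possibly, probably or definitely related to study drug, it is reported as an SAE.*

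This applies the sponsor's own test for deaths to admissions, and carries the Section 11.2 tie-break through to SAE status. The separate allowance in Section 11.2.3, under which "a period of normal hospitalisation will be outlined in the protocol or by the judgment of the Investigator", can stay as it is. If the Study Reference Manual already gives this rule, repeat it in the note so that the two agree.

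The cost is a short protocol amendment with written ethics committee approval (Section 14.1), a memo to sites, and some additional SAE forms for admissions that prove to be disease-related. It is a cheap improvement.

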11.2.4 Reporting Serious Adverse Events

SAEs will be reported promptly, using the SAE/MEOI Report Form, once the Investigator determines that the event meets the protocol definition of an SAE. The Investigator or designee will report the SAE **within 24 hours of his/her becoming aware of these events regardless of relationship of the SAE to the use of study drug**, in accordance with the instructions in the Study Reference Manual. The Investigator will always provide an assessment of relatedness at the time of the initial report as described in Section 11.2.2. The SAE Report will always be completed as thoroughly as possible with all available details of the event within the designated time frames. Copies of relevant patient records, autopsy reports, and other documents may be requested.

If the Investigator does not have all information regarding an SAE, he/she will not wait to receive additional information before reporting the SAE. The SAE Report will be updated when additional information is received **within 24 hours of receipt of such information**.

Important: For fatal and life-threatening events, the Sponsor's Medical Responsible Person should be contacted immediately. A death occurring during the study or information related to such occurrence that comes to the attention of the Investigator during the study must be reported immediately to the Sponsor.

Contact numbers will be provided to the site, with a detailed SAE reporting procedure to be included in the Study Reference Manual (SRM), before any patients are consented.

Table 7: Serious Adverse Event Reporting Contact Details

PPD	
Australia Safety (phone/fax)	PPD
Worldwide Safety (toll - phone/fax)	

Additionally, the Human Research Ethics Committee (HREC)* must be notified in writing of any SAEs that require expedited reporting to Regulatory Authorities. Depending upon regional requirements, it is the responsibility of either the Investigator or Imago BioSciences to notify the HREC. All unexpected SAEs (i.e. not documented in the current version of the Investigator Brochure) that are suspected by the Investigator to be related to the use of the study treatment (deemed possibly, probably or definitely related) will be reported to appropriate regulatory

agencies by Imago BioSciences or their designee as soon as possible and within the timeframes specified in the various regions in which the study is to be conducted.

* If additional countries are engaged outside of Australia, then for purposes of this protocol reference to HREC shall also be deemed reference to any other Institutional Review Board (IRB) or Independent Ethics Committee (IEC).

11.2.5 Medical Events of Interest (MEOIs)

Medical Events of Interest (MEOI) are AEs that do not meet any criteria for an SAE but are nonetheless of particular interest in the context of this study. Medical Events of Interest will be collected for all patients during the study period in an expedited manner using the SAE/MEOI Report Form and following the SAE reporting process (see Section 11.2.4). Although these are non-serious events, the Investigator will be asked to provide detailed initial information and follow-up to the Sponsor. The Sponsor will periodically review the AE data and in some cases may escalate an AE to a MEOI. Examples of MEOI and reporting times include, but are not limited, to the following:

Table 8: Examples of MEOI and Reporting Timelines

MEOI	Reporting Times
Electrocardiogram QT corrected interval prolonged 481 - 500 ms	Within 5 business days

12 ANALYSIS AND STATISTICAL CONSIDERATIONS

12.1 General Considerations

Detailed methodology for summary and statistical analyses of the data collected in this trial will be documented in a Statistical Analysis Plan (SAP). Additionally, a Pharmacokinetic Analysis Plan (PKAP) will be prepared. These documents may modify the plans outlined in the protocol; however, any major modifications of the primary endpoints definition and/or its analysis will also be reflected in a protocol amendment. Additional statistical analyses other than those described in this section may be performed if deemed appropriate and included in the SAP/PKAP.

12.2 Power

This study is designed to make an assessment of the safety, tolerability, and single-dose pharmacokinetics of the capsule formulation of IMG-7289, with and without ATRA. With the planned minimum number of patients per dose cohort/sub-cohort (N=3), the study is sufficiently powered to determine mean pharmacokinetic parameters. When feasible, more patients will be added to each cohort/sub-cohort.

12.3 Treatment Assignment and Blinding

This is an open-label study. The Investigators, other hospital personnel, patients and Sponsor will know the identity of the treatment.

Effort will be made, as appropriate, to maintain continuity of study staff who administer/evaluate various assessments at each site (i.e., physical examination, ECG, morphology review, etc.), in order to facilitate consistency of assessments within a patient.

12.4 Study Endpoints

12.4.1 Primary Endpoints

- The safety and tolerability of IMG-7289 with and without ATRA will be assessed by the analysis of adverse events (AEs), as well as changes in physical examinations, vital signs and laboratory values as detailed below.
 - Monitoring of Adverse Events (AEs) including determination of dose limiting toxicities (DLTs), medical events of interest (MEOIs), serious adverse events (SAEs), and AEs. AEs will be assessed in terms of onset, duration, seriousness, severity, and causality, using the National Cancer Institute Common Terminology Criteria for Adverse Events (NCI CTCAE), Version 4.03. Deaths and other serious adverse events (SAEs) will also be evaluated and will be collected on a separate case report form (CRF).
 - Changes in physical examinations, vital signs and laboratory values will also be evaluated and assessed. Information on the timing of these assessments is presented in Section 9. The following laboratory tests will be conducted:
 - Complete blood counts (CBC) and differential
 - Coagulation
 - Chemistry panel including LFTs (AST, ALT, INR, total bilirubin, gamma glutamyltransferase (GGT), and albumin)
 - Urinalysis with microscopy
 - Electrocardiograms
- Pharmacokinetic (PK) parameters will be determined using serial blood sampling at specified time points to determine PK effects of IMG-7289 with and without ATRA. Non-compartmental methods of analysis will be used to determine PK parameters following oral dosing of patients in Cycle 1. The following endpoints will be calculated: observed maximum concentration (C_{max}), the time at which C_{max} occurred (T_{max}), the area under the concentration-time curve from time 0 to 24 hours post-dose (AUC_{0-24}), the apparent total clearance of drug after oral administration (CL/F), the apparent volume of distribution during terminal phase after oral administration (V_z/F) the terminal disposition phase half-life ($t_{1/2}$), and the elimination rate constant (k_{el}).
- The adequacy of IMG-7289 dose and duration, with and without ATRA, in producing a pharmacodynamic effect will be determined using serial blood and bone marrow sampling throughout the course of treatment. Responses will be documented according to revised/modified International Working Group (IWG) Response Criteria – [Cheson *et al.* 2003](#) for AML and [Cheson *et al.* 2006](#) for MDS. Measures of response will be assessed by blood counts and simultaneous examination of the bone marrow for percentage of bone marrow blasts, as well as

cytogenetics and molecular studies of bone marrow mononuclear cells.

- Pharmacodynamic (PD) measurements will be obtained from serial blood, bone marrow, and urine sampling at specified time points to describe the PD effects of IMG-7289 with and without ATRA. The following endpoints may be analyzed: CCI

CCI

CCI

